11.5 Please provide a justification for your sample size

Power was calculated using repeated Monte Carlo Markov Chain simulations predicting 3-month VISA-A between treatment arms, and sourced assumptions of mean and spread from Tumilty et al (2016). MCID was considered to be a 6.5 point difference in VISA-A¹⁴.

11.6 Data Analysis Plan: Complete description: Background, Objectives, Design, Step by Step how the project is going to be done, Data analysis plan:

Outliers will be removed if determined to be erroneous based on relevant clinical expertise. Data will be analyzed on a complete-case intention-to-treat (ITT) basis. Confounding will be principally controlled by randomization. In order to increase the precision of our estimates, we may also statistically adjust for patient demographics and relevant clinical variables.

Methods to be used for the Primary Aim: Time-to-event analyses (return to activity) will use survival analysis. All other outcome measures (including our primary outcome measure (VISA-A) and other aforementioned secondary outcome measures) will be analyzed using generalized additive models predicting change in each outcome measure by treatment group at 3 months. Sensitivity analyses for non-time-to-event outcome measures will be performed to evaluate trends by treatment group and will use longitudinal hierarchical/multilevel models incorporating random effects to account for repeated measures. Analyses under the primary aim will use the initial 3-month cohort only.

Methods to be used for the Secondary Aim: Due to the lack of washout period between initial and cross-over periods, as well as the removal of patient blinding (patients may choose the specific treatment they wish to receive during this final 3-month period), cross-over response will be analyzed and treated as an exploratory aim versus an inferential aim. Due to the exploratory nature of this aim, additional or adjusted analyses may be performed to best explore and evaluate the data collected. Generalized additive models will be used and a limited set of measures will be explored (patient satisfaction, functional tests, ultrasound measures).

Hypothesis tests will be two-tailed and statistical significance will be considered at the putative threshold ($\alpha=0.05$). P-values (outside of analysis of primary outcome) will be subject to a false discovery rate adjustment in keeping with best statistical practices. Multilevel models will incorporate random effects to account for repeated measures, using distribution families and link functions appropriate for the outcomes of interest, determined using QQ plots analyzed for best model fit. All statistical analyses will be performed using the R Programming language.

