Extracorporeal shockwave therapy (ESWT or SWT) is a process in which energy is delivered to the muscles or tendons for pain relief.⁷ A recent network meta-analysis showed that ESWT is effective in treating AT when combined with ECC.¹ Moreover, a recent narrative review presented ESWT as an effective treatment for specific tendinopathies, including AT.⁸ Notably PBMT was not able to be compared in the analysis due to no published studies meeting criteria for inclusion. There is also limited information available on the best energy settings to be used in treating AT and the impacts on short term recovery;¹ therefore more research needs to be done into the impact of ESWT on treating AT.

Photobiomodulation therapy (PBMT) and ESWT are effective tendinopathy treatments, and a study on the treatment of other tendons in the body - lateral epicondylitis (tennis elbow) - showed improvement in both the PBMT and the ESWT arms, with ESWT showing a significant difference in increasing handgrip strength.⁹ Studies such as this are promising that ESWT and PBMT will be effective in treating other tendon injuries such as AT, however, these treatment methods have not been evaluated in comparison or combination with each other. Promising results from these studies combined with the previous unclarity in the best treatment for AT justifies the need for more research.

This combination of treatment (SWT + PBMT) may provide improved healing over siloed modalities. ESWT works by creating microtears that in turn stimulate the body's inflammatory response and healing cascade.⁷ PBMT could then increase this cascade further by increasing the cellular function, particularly when the body is in an inflamed state, such as the state after ESWT.^{2,6} Thus, this treatment combination should be explored.

The sub-section of AT amongst Active-Duty (AD) personnel has had very limited research and given the high prevalence, should be addressed. Therefore, our study will compare four different treatment arms utilizing traditional physical therapy (PT), PT plus shockwave therapy (SWT), PT plus PBMT, and PT plus SWT and PBMT. Both self-reported questionnaires and measured outcomes will be used to assess the most effective treatment for AT.

9.3

Objectives/Specific Aims/Research Questions:

Describe the purpose and objective(s) of the study, specific aims, and/or research questions /hypotheses

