The primary aim is to evaluate the effects of standard PT compared to PT with SWT, PT with PBMT, and PT with a combination of SWT and PBMT in the management of AT. *We hypothesize servicemembers in each treatment allocation will see improvement in functional outcomes, pain and measures of Achilles tendon structure compared to baseline measures. As SWT and PBMT may change structural properties and modulate pain in tendinopathy, we anticipate greater measures in activity function for participants assigned to SWT and PBMT over PT as sole treatment.*

The secondary outcome will be to evaluate cross-over response. After the initial 3-month randomized control trial, participants who are not satisfied with results will be able to select a different treatment arm for the remaining 3 months of the study.

9.4 Study Design:

Describe study design in one to two sentences (e.g., prospective, use of existing records/data /specimens, observational, cross-sectional, interventional, randomized, placebo-controlled, cohort, etc.). Specify the phase – Phase I, II, III, or IV – for FDA-regulated investigational drug research

A Randomized Control Trial with Elective Cross-Over Design

9.5 Target Population:

Describe the population to whom the study findings will be generalized

Active-Duty Service Members (ADSMs) and the active civilian runner population

9.6 Benefit to the DoD:

State how this study will impact or be of benefit to the Department of Defense

AT is a common overuse running injury among ADSMs that can impact their combat readiness throughout their military career. Current rehabilitation treatment plans include ECC, but its success rate is limited leaving approximately 40% without full relief of pain and symptoms and decreased activity levels. The use of SWT, PBMT, or both SWT and PBMT along with physical therapy on ADSM with AT, may improve their recovery time. Faster healing translates to quicker return to higher level activities, return to duty (RTD), and ultimately mission ready status.

10.0

Study Procedures, Data Management, and Privacy

10.1 Study Procedures:

Describe step-by-step how the study will be conducted from beginning to end

The study procedures will take place in the Physical Therapy, Sports and Exercise Medicine, and Orthopaedic and Podiatry Clinics.

Recruitment, Pre-Screening (before consent), Study Introduction & Informed Consent:

Potential participants will be identified via four methods:

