Multilevel models will incorporate random effects to account for repeated measures, using distribution families and link functions appropriate for the outcomes of interest, determined using QQ plots analyzed for best model fit. All statistical analyses will be performed using the R Programming language.

11.2 Sample Size:

We are requesting to enroll 160 total participants (40 per initial treatment arm) after adjusting for screen failures and attrition for a final sample of at least 112 (28 per initial treatment arm). 35 patients in each initial treatment group (140 patients total) will achieve 90% power to detect an effect size of 16 points. 30 patients in each initial treatment group (120 patients total) will achieve 90% power to detect an effect size of 17 points. 25 patients in each initial treatment group (100 patients total) will achieve 90% power to detect an effect size of 18 points. Effect size for the purpose of power calculations was defined as the difference between VISA-A at 3 months between PT only and PT + Additional Treatment (assumptions were based on PT + PBMT due to availability of comparable historical research), with statistical significance defined as $\alpha = 0.05$.

11.3 Total number of subjects requested (including records and specimens):

160

11.4 If you are recruiting by study arm, please identify the arms of the study and how many subjects will be enrolled in each arm

Across all performance sites, up to 160 participants will be randomized 1:1:1:1 to the four initial treatment arms (40 participants per arm)

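### Does the VISA-A analysis need its contrasts named, with the combination-versus-single comparison designated?

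*Combined protocol and SAP*

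**What the plan says.** The methods for the primary aim, in sections 11.1 and 11.6, analyse VISA-A and the other outcomes that are not time-to-event with "generalized additive models predicting change in each outcome measure by treatment group at 3 months". No reference arm, contrast, global test or testing order is given there. On multiplicity, section 11.6 states that "P-values (outside of analysis of primary outcome) will be subject to a false discovery rate adjustment", with two-sided tests at 0.05.

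The comparisons of interest are set out elsewhere. Section 9.3 gives the primary aim as to "evaluate the effects of standard PT compared to PT with SWT, PT with PBMT, and PT with a combination of SWT and PBMT", and its hypothesis anticipates an advantage of the add-on treatments over PT alone. Section 11.2 defines the effect for the power calculation as "the difference between VISA-A at 3 months between PT only and PT + Additional Treatment".

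Some wording is broader. Section 9.2 says "our study will compare four different treatment arms" and "Both self-reported questionnaires and measured outcomes will be used to assess the most effective treatment for AT". It gives the reason for the fourth arm as "This combination of treatment (SWT + PBMT) may provide improved healing over siloed modalities". Section 11.5 refers to "simulations predicting 3-month VISA-A between treatment arms".

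**The concern.** An analysis section that fits one term for a four-level treatment factor does not say which differences will be tested. Because the primary outcome is exempt from the false discovery rate adjustment, the number of contrasts run on VISA-A sets the error rate directly. If that number were open until the data were seen, so would be the chance of a false claim on the primary outcome.

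The combination arm adds to the worry. Its rationale is that two modalities together may do better than either alone, yet no aim, hypothesis, power statement or analysis sentence takes up that comparison. If it were tested on VISA-A at an unadjusted 0.05, a chance difference could be presented as evidence on the question that motivated the arm. The natural remedy would be to name three primary contrasts with PT and make the combination against each single modality a secondary family of two under a false discovery rate adjustment.

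**Working it through.** **1. The plan's own figures.** Section 11.2 gives 90% power at two-sided 0.05 for 16 points with 35 per arm, 17 with 30 and 18 with 25. No SD is stated, so it has to be back-solved. By the normal approximation, SD = d × √(n/2) / (1.960 + 1.282):

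- 35 per arm: 16 × 4.183 / 3.242 = 20.65
- 30 per arm: 17 × 3.873 / 3.242 = 20.31
- 25 per arm: 18 × 3.536 / 3.242 = 19.63

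With the t distribution the values are 20.35, 19.97 and 19.24. A single SD of 20.2 returns power of 0.912, 0.903 and 0.883. The rows therefore fit one unadjusted two-arm comparison with PT. They do not prove that this test was simulated, because other tests fit about as well with a different SD. The final sample of 112 is 160 × (1 − 0.30), or 28 per arm.

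**2. False-positive rates on VISA-A when no arm differs.** Simulated with 28 per arm, normal outcomes, pooled variance (108 df) and two-sided 0.05. These rates do not depend on the SD.

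| Tests run | Any false positive |
|---|---|
| Omnibus, 3 df | 5.0% |
| Three add-on arms against PT | 12.5% |
| Combination against each single modality (two tests) | 9.0% |
| Those five | 18.0% |
| All six pairs | 20.1% |
| Three against PT, plus the two in a Benjamini-Hochberg family | 15.1% |

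As a check, three independent tests would give 1 − 0.95³ = 14.3%. Sharing the PT arm brings this down to 12.5%. With 40 per arm the rates change by 0.1 point or less.

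**3. Which row applies.** The model sentence stands in the paragraph on methods for the primary aim. Section 9.3 defines that aim as PT against each of three arms, and section 11.2 sizes that comparison. The phrase in section 11.5 describes the simulation whose effect section 11.2 defines against PT, so it is not evidence for pairwise testing. The remaining support for all pairs is general language in the background section. The omnibus reading rests only on the model being fitted by treatment group. The second row is the one that the protocol describes.

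**4. If the combination were tested against each single modality.** Assume that all three add-on arms are 17 points better than PT and the combination adds nothing over a single modality. Two unadjusted tests then give a false difference in about 9% of trials. That count covers both directions: the combination appears better than at least one single modality in about 4.5% of trials, and better than both in about 0.5%.

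**5. What designation would bring.** Precision at 28 per arm is t × SD × √(2/28) = 1.982 × SD × 0.267. This is ±10.2 points at SD 19.24 and ±10.8 at 20.35, against the plan's MCID of 6.5. At SD 20.2, power at 6.5 points is about 22%, and 90% power needs 20.2 × 0.267 × 3.242 = 17.5 points.

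Now assume that the combination is truly 10 points better than each single modality. The adjusted family of two lowers the chance of showing a difference from at least one of them from about 65% to 54.5% (SD 19.24), or from about 61% to 50% (SD 20.35). The chance of showing a difference from both is 28% to 32% with or without the adjustment.

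**The case for a change.** The strongest case for a change is that a statistical section should be complete in itself. Section 11.1 asks for methods and variables for each analysis, consistent with the objectives. Section 9.3 does not rule out further contrasts, and section 9.2 promises a four-arm comparison and a view on the most effective treatment. Three sentences written before the data are seen would cost no patients or visits and would remove any room for a later choice.

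Part of this stands. Sections 11.1 and 11.6 do not restate the contrasts, the combination-versus-single comparison has no label, and every VISA-A p-value is outside the adjustment. A cross-reference to section 9.3 would do no harm.

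It would not change the analysis, however, because the primary aim already identifies the three contrasts. Nor is the combination-versus-single comparison unusually exposed. Each contrast carries 5%, the two together carry less (9.0%) than the three with PT (12.5%), and on secondary outcomes the adjustment would cover such a comparison if it were tested. The one stated rule with a real consequence is the lack of adjustment across the three PT contrasts. Naming them leaves that 12.5% where it is.

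**Conclusion.** No change is needed. The missing list of contrasts is a gap in wording that sections 9.3 and 11.2 fill: three comparisons with PT only, with a 12.5% chance of at least one false positive if no arm differs and each is tested at 0.05. The 5% to 20% range arises only if the analysis sections are read apart from the aim they serve.

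The combination-versus-single comparison is background rationale, not a scheduled test, so the 9% figure belongs to an analysis that the plan does not contain. Making it a tested secondary family would add false-positive risk (12.5% to 15.1%) for estimates too imprecise to settle differences near 6.5 points. The same differences can be read, with their uncertainty, from the four-arm model already planned. If they are reported, they are best taken as exploratory.

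The error rates rest on normal outcomes, equal variances and 28 to 40 per arm. The interval widths and power figures also rest on a back-solved SD of 19.2 to 20.4 (20.2 where a single value is used). How the three PT contrasts should share 0.05 is a separate matter, not decided here.

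### Section 11.6 exempts the primary outcome from the plan's only multiplicity rule, yet the primary aim compares PT with three add-on arms and no contrast rule is stated

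*Combined protocol and SAP*

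**What the plan says.** Section 11.6 sets the general test level: "Hypothesis tests will be two-tailed and statistical significance will be considered at the putative threshold", with alpha given as 0.05. It then limits the multiplicity adjustment: "P-values (outside of analysis of primary outcome) will be subject to a false discovery rate adjustment in keeping with best statistical practices". No other multiplicity rule appears in 11.1, 11.2, 11.5 or 11.6.

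The primary outcome is VISA-A. It and the other non-time-to-event measures "will be analyzed using generalized additive models predicting change in each outcome measure by treatment group at 3 months". Neither 11.1 nor 11.6 says which group comparison decides the primary question.

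Three other places bear on that:

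- **Section 9.3, primary aim:** the trial will "evaluate the effects of standard PT compared to PT with SWT, PT with PBMT, and PT with a combination of SWT and PBMT". That is one reference arm and three comparators.
- **Section 9.3, hypothesis:** "we anticipate greater measures in activity function for participants assigned to SWT and PBMT over PT as sole treatment". This can mean each add-on, or only the arm that receives both.
- **Section 11.2, sample size:** the effect is "the difference between VISA-A at 3 months between PT only and PT + Additional Treatment", at alpha 0.05, with planning assumptions taken from PT + PBMT because comparable historical research was available. Power is 90% for 16, 17 and 18 points with 35, 30 and 25 per arm.

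The final sample is planned as at least 28 per arm (112 in total) from 40 per arm enrolled.

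**The concern.** Leaving a primary outcome out of an FDR adjustment is ordinary when that outcome rests on one test. Here the exemption covers an outcome with three natural comparisons against a shared control, and nothing replaces the adjustment it removes. The rule for calling the trial positive could be three pairwise tests, one overall group test, or a single contrast, and the choice could be made after the data are seen. Under at least one permitted choice, the error rate of the primary claim is well above 5%. The stated 90% power also cannot be tied to the primary claim until the rule is known.

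**Working it through.** **1. The plan's own power figures.** The documents give no SD, and 11.5 says only that "Power was calculated using repeated Monte Carlo Markov Chain simulations predicting 3-month VISA-A between treatment arms", with mean and spread from a cited trial. The 90% therefore cannot be reproduced directly. What can be checked is the SD it implies for one two-sided contrast at undivided 0.05:

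SD = d / [√(2/n) × (1.960 + 1.282)]

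| n per arm | d (points) | SD, normal formula | SD, noncentral t (4n − 4 df) |
|---|---|---|---|
| 35 | 16 | 20.65 | 20.50 |
| 30 | 17 | 20.31 | 20.14 |
| 25 | 18 | 19.63 | 19.44 |

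One SD near 20 fits all three rows: the normal formula gives 91.7%, 90.9% and 88.9%. The figures agree with a single unadjusted contrast.

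**2. All arms equal, three tests against PT.** Inputs: two-sided 0.05 (11.6), 1:1:1:1 allocation (11.4), 28 per arm (11.2). The model is four normal arms with pooled variance, df = 4 × 28 − 4 = 108 and critical value c = 1.982. This approximates the planned generalized additive model. Each contrast has variance 2σ²/n, and two contrasts share the PT arm with covariance σ²/n, so their correlation is 0.5. Then

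P(at least one |T| > c) = 1 − E over s of ∫ φ(x) [Φ(x + cs√2) − Φ(x − cs√2)]³ dx,

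where s is the ratio of estimated to true SD. For false benefit only, drop the second Φ term.

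- At least one false rejection: 12.48% by integration, 12.5% by simulation.
- At least one false claim that an add-on beats PT: 6.24% by integration, 6.2% by simulation. A single test gives 2.5%.
- Neither figure depends on the SD, and at 25 to 40 per arm both move by no more than about 0.1 point.
- The independence formula, 1 − 0.95³ = 14.3%, does not apply because the control arm is shared.

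Other rules the text allows, all arms equal: an F test at 0.05 as a gate before the three contrasts gives about 4% (any false rejection) and 2% (false benefit); all six pairwise tests at 0.05 give about 20% for any false rejection.

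**3. One add-on works, two do not.** Simulation at 28 per arm. The SD is assumed to be 17 to 20.5. Rates are for at least one error among the two null add-ons.

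| True effect of the working add-on | Ungated: any / false benefit | F gate: any / false benefit |
|---|---|---|
| 6.5 points | about 9% / 4.5% | 5.4–6.3% / 2.7–3.1% |
| 16–18 points | about 9% / 4.5% | about 9% / 4.5% |

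The first row is the plan's own threshold ("MCID was considered to be a 6.5 point difference in VISA-A"). The second row is the range 11.2 was powered for. There the working arm almost always opens the gate, so the gate gives the null arms hardly any protection.

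**4. What Dunnett control would cost.** Noncentral t, 4n − 4 df, Dunnett critical values 2.376, 2.380 and 2.387, with one common SD assumed across rows. Each cell shows power unadjusted → Dunnett.

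| SD | 35 per arm, 16 points | 30 per arm, 17 points | 25 per arm, 18 points |
|---|---|---|---|
| 19.5 | 92.6 → 85.3% | 91.7 → 83.9% | 89.8 → 80.8% |
| 20 | 91.4 → 83.3% | 90.4 → 81.8% | 88.3 → 78.5% |
| 20.5 | 90.0 → 81.2% | 89.0 → 79.6% | 86.7 → 76.2% |

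The loss runs from 92.6 − 85.3 = 7.3 points to 86.7 − 76.2 = 10.5 points.

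**The case against.** **The plan does not commit to three tests.** This stands. A comparison by treatment group also describes one overall test, which holds 5% when all arms are equal. A reader might infer that the trial's error rate is 12.5%. The documents do not support that: it is the rate under one permitted reading, neither a bound nor the plan's own figure. What is certain is that the rule is missing and that the exemption is explicit.

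**Much is already fixed.** This also stands. A reader might infer that the whole primary claim is open. It is not: 11.6 fixes VISA-A, 3 months, the model class, two-sided 0.05 and the initial 3-month cohort.

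**The sample-size section names the contrast, or has already allowed for several.** Neither holds. PT + PBMT is the source of the planning assumptions, chosen for available data; it is not designated as the confirmatory comparison. A smaller SD (about 17 to 18) would reproduce the same power at a divided alpha, but 11.2 defines significance as alpha = 0.05, so the plain reading is one contrast at undivided alpha.

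**Distinct treatments sharing a control need no family-wise control.** Practice is debated, and the exemption may be deliberate. The argument is weaker here because one arm combines the other two add-ons and all three serve one stated aim. If that is the sponsor's position, the plan should say so and say what each claim means.

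**The two-sided rates overstate the practical harm.** Partly fair. A false claim of benefit is half as likely as any false rejection, which is why both are shown. It still exceeds 2.5% in every ungated case.

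**Conclusion.** The concern holds as a missing decision rule on the primary outcome, made material by an explicit exemption from the only multiplicity rule. With three ungated tests and all arms equal, the error is about 12.5% for any false rejection and 6.2% for a false claim of benefit. If one add-on works, it is about 9% and 4.5% among the two that do not, and an F gate does not repair this at 16 to 18 points.

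The equal-arms figures rest on equal allocation, normal errors and a pooled variance, not on the SD. The gated one-arm-works figures and the power figures also rest on assumed SDs, since the documents give none. This should be settled before results are seen, because a contrast rule chosen afterwards cannot be defended.

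**What to change.** **In 11.6**, adopt one of two rules for VISA-A at 3 months:

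- **(a)** Name the three contrasts with PT only as the primary family and control its error at two-sided 5%, with either Dunnett-adjusted p-values and simultaneous 95% confidence intervals or a pre-specified fixed sequence.
- **(b)** Name one contrast as primary, and reword the exemption so that the other two VISA-A contrasts fall under the FDR rule. As now worded, the exemption would still shelter them.

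If an overall group test is meant as a gate, state it and still control the pairwise contrasts. Keep FDR for secondary outcomes.

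**In 11.2**, state that the 90% power is for one contrast at alpha = 0.05, give the SD used, and rerun the existing simulation under the chosen rule.

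**Cost.** The work is wording in two sections and one rerun. Under Dunnett, power falls by roughly 7 to 11 points, to about 76–85% across the listed scenarios for a common SD of 19.5 to 20.5. Option (b) costs the named contrast no power. A fixed sequence costs its first contrast none, but allows no claim on later contrasts after a failure. No extra patients are needed if the restated power is accepted.
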